Design	
This is a phase II, multi-center, randomized, double-masked, parallel-arm, vehicle-controlled, prospective clinical trial to evaluate the safety and efficacy of two concentrations (C mcg/mL and C mcg/mL) of a new formulation of rhNGF ophthalmic solution, administered as one (1) drop three (3) times a day in both eyes, for four (4) weeks in patients with DED.
 
Patients will be evaluated at screening visit (day -12±2 - Visit 1), baseline (day 1 - Visit 2), week 2 (day 13±1- Visit 3), week 4 End of Treatment (EOT; day 28±1 - Visit 4), and week 8 end of follow-up and End of Study (EOS; day 56±2- Visit 5). An Early Exit visit could be performed in case of premature study discontinuation.
 
The study duration per each patient will be of maximum 10 weeks, and it is divided into four phases as follows:
 
1. Screening & Start of Run-In (day -12±2, Visit 1):
 
Procedures for inclusion will be performed at both Visit 1 (Screening) and Visit 2 (Baseline).
 
At Visit 1, eligible patients will be instructed to discontinue all topical ophthalmic medications and during the Run-In period they will only be allowed to use Study Product (vehicle) ophthalmic solution provided by the Sponsor.
 
The first eye drop of the Study Product (vehicle) will be applied, in both eyes of patients, at the site by the investigator during Visit 1. Patients will be instructed on how to prepare the Study Product (vehicle) daily at home and then how to self-administer one drop 3 times a day in both eyes.
 
A Patient Diary for the Run-In phase will be supplied to the patient. Investigators will document the first administration of the Study Product (vehicle) in the patient's medical record following Visit 1 to confirm the first administration of the Study Product (vehicle).
 
2. Run-In Period (day -12±2 Screening Visit 1 to day 1/Baseline Visit 2):

Information	Description

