4.4.1. Baseline

For the purpose of the statistical analysis, Baseline is defined as the last visit prior to and including date of the randomization visit (V2 – Day 1). Unless otherwise specified, baseline values are defined as the measurements taken during this visit. In case of multiple measurements

during baseline visit, the last assessment will be considered as the baseline evaluation. In case of missing value at baseline visit, but availability of other values collected before the first administration of the IMP (e.g. at Screening), the last available value collected will be used as the baseline value.

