8.1.1. Primary Analysis

The overall null hypothesis H_0 is that the change from baseline in the SANDE Global Score for both of the two concentrations of rhNGF ophthalmic solution (μ_{DOSE5} and μ_{DOSE10}) are greater or equal (worse and no improvement, respectively) than the vehicle one ($\mu_{VEHICLE}$):

$$H_0 = \mu_{DOSE5} \geq \mu_{VEHICLE} \text{ and } \mu_{DOSE10} \geq \mu_{VEHICLE}$$

$$H_1 = \mu_{DOSE5} < \mu_{VEHICLE} \text{ or } \mu_{DOSE10} < \mu_{VEHICLE}$$

where μ denotes the mean change from baseline at week 8 in SANDE global score. For SANDE global Score, lower score is better.

Considering the multiple comparisons (rhNGF 5 mcg/mL versus vehicle, and rhNGF 10 mcg/mL versus vehicle) to claim overall superiority, a Bonferroni multiplicity correction of type I error will be applied on multiple comparisons. Each comparison will be consequently tested at one-sided alpha = 0.0125, in order to preserve the overall one-sided alpha of 0.025. The overall null hypothesis H_0 will be rejected if the associated primary analysis one-sided p-value will be lower than 0.0125 for one of two comparisons or both comparisons.

The primary analysis will be performed via Mixed-effects Model for Repeated Measures (MMRM) in the FAS according to the planned treatment. The analyses will include the change from baseline in SANDE global score as the dependent variable; the fixed effects of treatment (3 levels: rhNGF 5 mcg/mL, rhNGF 10 mcg/mL, and vehicle), visit (2 levels: Week 4, Week 8), baseline value, and treatment by visit interaction. An “unstructured” covariance matrix will be used. If the model fails to converge by using unstructured covariance matrix, compound symmetry matrix will be used instead. Each treatment group (IMP1 and IMP2) will be compared with the vehicle group at Week 8 using the difference in least square means (LS means) (i.e. difference between each concentration group and vehicle in mean change from baseline). The model can be summarized as follows:

$$\text{change from baseline} = \beta_0 + \beta_1 \text{treatment} + \beta_2 \text{base} + \beta_3 \text{visit} + \beta_4 \text{treatment} * \text{visit} + \varepsilon$$

where $\varepsilon \sim N(0, R)$ and R is the “unstructured” covariance matrix with blocks defined by the patients.

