Missing data will be imputed by using a multiple imputation with copy-reference approach (see [Section 8.1.1](#)). For each imputed dataset, the change from baseline at Week 4 is derived. Patients with change from baseline at Week 4 ≥ 10 mm/5min will be considered as having improvement while patients with change from baseline at Week 4 < 10 mm/5mins will be considered as not having improvement. 95% CI on proportion of patients having improvement will be implemented by using Clopper Pearson method.

The derived binary variable described in the previous step will then be used in a logistic model as dependent variable; treatment (3 levels: rhNGF \blacksquare mcg/mL, rhNGF \blacksquare mcg/mL, and vehicle) and baseline Schirmer-I scores in the Study Eye as covariates.

Based on this modeling, the estimated proportions and corresponding two-sided 95% CI will be provided for each treatment arm; the estimated mean proportion differences, two-sided 95% CI, and corresponding one-sided p-value will be provided for each IMP group versus vehicle at Week 4.

8.2.1.2. Mean change from baseline in Schirmer-I score without anesthesia in the Study Eye at Week 4

The MI procedure described in [Section 8.2.1.1](#) will be applied to impute missing Schirmer-I scores at Week 4. Change from baseline at Week 4 will be fitted in the ANCOVA model with change from baseline at Week 4 as dependent variable, treatment (3 levels: rhNGF \blacksquare mcg/mL, rhNGF \blacksquare mcg/mL, and vehicle) and baseline Schirmer-I scores in the Study Eye as covariates.

Based on this modeling, a point estimate (the adjusted estimated treatment effect), associate SE, two-sided 95% CI, and corresponding one-sided p-value will be provided for each treatment group; a point estimate (the adjusted estimated treatment difference), associate SE, two-sided 95% CI, and corresponding one-sided p-value will be provided for each least squares (LS) mean treatment difference versus placebo at Week 4.

8.2.1.3. Mean change from baseline in total corneal fluorescein staining (NEI scale) in the Study Eye as assessed by the investigator at week 4

Corneal fluorescein staining has 5 zones and each zone has a score range of 0-3. The total score is determined by simply adding up the scores of the 5 individual zones. The range of total corneal fluorescein staining in NEI scale is 0-15. If any of the 5 individual zones has a missing score, the total score would be missing.

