13.3. SAS Code for Primary Analysis

Step 1: Multiple Imputation

```
PROC SORT data=efficacy;  
  by USUBJID;  
RUN;
```

```
PROC MI data=efficacy nimpute=50 out=mi_data min=0 max=100 seed= 47292748; *score range: 0-100;  
  class TRTPN;  
  var V2 V4 V5; *V2=baseline, V4=Week 4, V5=Week 8;  
  FCS regression;  
  mnar model(V2 V4 V5/ modelobs=(TRTPN='3')); *Vehicle group has TRTPN=3;  
RUN;
```

Data will be transformed to short format by AVISITN before applying multiple imputation.
The MI method will be used for both primary and secondary analyses after applying appropriate ICE handling strategies.

Step 2: MMRM Model

```
PROC MIXED data= mi_data_long;  
  by _imputation;  
  class TRTPN AVISITN USUBJID;  
  model CHG=BASE TRTPN AVISITN TRTPN*AVISITN / DDFM=KR CL;  
  repeated AVISITN/subject=USUBJID type=UN;  
  lsmeans TRTPN*AVISITN/diff cl;  
  ods output lsmeans=lsM diffs=diffM;  
RUN;
```

Data will be transformed back to long format by combining visits before applying MMRM model.
If model fails to converge, the “type=UN” will be replaced by “type=CS”.
This model is the essential model for primary endpoint. Appropriate adjustments may be made based on modified Estimand strategies and sensitivity analyses.

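### Free improvement: the primary and key secondary models adjust only for the Visit 2 value, although the same measures are also taken before randomisation at Visit 1

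*SAP*

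**What the plan says.** - **Primary model.** SAP 8.1.1 and Protocol 10.6.2 specify an MMRM with one pre-treatment covariate. Besides treatment, the SAP lists the fixed effects as "visit (2 levels: Week 4, Week 8), baseline value, and treatment by visit interaction". The code in SAP 13.3 reads "model CHG=BASE TRTPN AVISITN TRTPN*AVISITN / DDFM=KR CL".
- **Key secondary models.** SAP 8.2.1 fits the Schirmer-I logistic model and ANCOVA with treatment and "baseline Schirmer-I scores in the Study Eye as covariates". The staining ANCOVA repeats that method with its own baseline. Protocol 10.6.4 agrees.
- **Imputation.** The PROC MI step in SAP 13.3 uses "var V2 V4 V5; *V2=baseline, V4=Week 4, V5=Week 8". Visit 1 is absent.
- **Meaning of baseline.** SAP 4.4.1: "Baseline is defined as the last visit prior to and including date of the randomization visit", that is, Visit 2 on Day 1. If that value is missing but an earlier pre-dose value exists, "the last available value collected will be used as the baseline value". In the readable text this is the only analysis role for a Visit 1 reading.
- **What Visit 1 collects.** Protocol 8.1 and Table 1 schedule SANDE, Schirmer-I and NEI corneal staining at both Visit 1 and Visit 2, with the ocular tests done in each eye. Protocol 1.1: "Procedures for inclusion will be performed at both Visit 1 (Screening) and Visit 2 (Baseline".

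No unredacted text gives a reason for leaving Visit 1 out of the models.

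**The concern.** Eligibility is checked at both visits, so nearly every randomised patient should have two pre-treatment readings of the primary endpoint measure and of all three key secondary measures. The models use one.

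A single reading is a noisy measure of a patient's level. For SANDE (at least 50) and Schirmer-I (above 2 and below 10 mm) the entry limits also compress its range, which weakens it as a covariate. For Schirmer-I there is a further reason: the study eye is chosen at Visit 2 as the eye with the lower score (SAP 3.6). When both eyes qualify, the Visit 2 study-eye value is therefore partly selected on its own error. The Visit 1 reading of that eye is not selected in this way.

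At stake is precision in the two dose comparisons on the primary endpoint, and in the key secondary tests that they gate.

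**Working it through.** **1. The plan's own figure.** Protocol 10.1 gives mean changes of -28.2 and -17.4 (difference 10.8), SDs of 26.36 and 20.29, one-sided alpha 0.0125 per comparison, and 92 evaluable patients per group.

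- SE = sqrt((26.36² + 20.29²)/92) = sqrt(1106.53/92) = 3.468
- z = 10.8/3.468 = 3.114
- Power = Φ(3.114 - 2.241) = 80.9%. A Welch t calculation gives 80.2%, and 92 is the smallest n that reaches 80%.

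So the stated 92 reproduces for a single comparison. The calculation uses SDs of observed changes with no covariate, and the sample size therefore does not rely on adjustment.

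**2. Closed form for a second covariate.** If Visit 1, Visit 2 and the outcome share one correlation ρ and there is no truncation, the residual variance with both readings relative to Visit 2 alone is (1 + 2ρ)/(1 + ρ)². At ρ = 0.5 this is 2/2.25 = 0.889, a cut of 11%. For ρ from 0.4 to 0.7 the cut is 8% to 17%. The gain is zero when the Visit 1-outcome correlation equals the product of the Visit 1-Visit 2 and Visit 2-outcome correlations.

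**3. With the entry limit.** Assumed: SANDE mean 65, SD 20, clipped to 0-100, patients kept only if at least 50 at both visits. None of these values comes from the documents except the limit of 50 and the scale range. Correlations are those before selection.

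| V1-V2 | V1-W8 | V2-W8 | Cut in Week 8 residual variance |
|---|---|---|---|
| 0.4 | 0.4 | 0.4 | 5.1% |
| 0.5 | 0.5 | 0.5 | 7.4% |
| 0.6 | 0.6 | 0.6 | 9.9% |
| 0.7 | 0.7 | 0.7 | 12.8% |
| 0.5 | 0.4 | 0.5 | 2.6% |
| 0.7 | 0.6 | 0.7 | 3.5% |
| 0.6 | 0.4 | 0.5 | 1.5% |
| 0.6 | 0.3 | 0.5 | 0.0% |

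Equal prediction gives about 5-13%. Weaker prediction by Visit 1 gives about 0-4%.

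**4. Power from the right starting point.** Because the planning SDs are raw change-score SDs, the planned MMRM, which already adjusts for Visit 2, has more power than step 1 shows. Let f be the residual variance divided by the raw change variance in the same simulation. Power is then Φ(3.114/sqrt(f) - 2.241).

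| Correlations | f, Visit 2 only | Power | f, Visits 1 and 2 | Power |
|---|---|---|---|---|
| all 0.4 | 0.785 | 89.8% | 0.745 | 91.4% |
| all 0.5 | 0.812 | 88.8% | 0.752 | 91.1% |
| all 0.7 | 0.873 | 86.2% | 0.761 | 90.8% |
| 0.7/0.6/0.7 | 0.895 | 85.3% | 0.864 | 86.6% |
| 0.6/0.3/0.5 | 0.850 | 87.2% | 0.850 | 87.2% |

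Planned power per dose is about 85-90%, and the addition is worth about 0-5 points.

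**The case against.** The strongest reply is that nothing in the plan is wrong. Adjusting for one prespecified baseline, the same value that defines the change score, is standard, and protocol and SAP agree on it. That stands, and it is why this is offered as an improvement.

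A second reply concerns how much Visit 1 can add. Visit 1 comes before patients stop their topical ophthalmic medication, and Protocol 4.2 describes the run-in as serving wash-out. Visit 1 is also further in time from Week 8. It may well predict less than Visit 2 does. This also stands: the lower end of the range is zero.

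A reader might infer that the trial sits at about 81% power and would be lifted to 83-86%. The documents do not support that starting point. The SDs in Protocol 10.1 belong to observed mean changes, not to residuals after Visit 2 adjustment, so 81% is not the power of the planned model.

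Two technical replies narrow the fix without removing it. In the logistic model an added covariate changes the conditional odds ratio, whereas the estimand in SAP 3.3.2 is a difference in proportions, and no gain has been quantified for that test. And where Visit 2 is missing, SAP 4.4.1 makes the Visit 1 reading the baseline, so the two covariates coincide for that patient.

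**Conclusion.** The omission is certain from the text. It costs some efficiency but leaves validity, alpha and the stated sample size intact. It should not be read as a defect in the primary test, nor as evidence that the trial is underpowered.

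The benefit is a reduction of about 0-13% in the Week 8 SANDE residual variance, and about 0-5 points of power per dose on a base of about 85-90%. Both ranges rest on assumed correlations and an assumed SANDE distribution, and the power range also on reading the planning SDs as raw change-score SDs. Confidence is high on the omission and moderate on the size of the gain. For the Schirmer-I and staining endpoints the direction is the same for the linear models, but the documents do not allow a firm figure.

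The change is still worth making. A pre-randomisation covariate does not bias the randomised comparison in a linear model, and the possible gain falls on the test that gates all the key secondary tests.

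**What to change.** Before unmasking, amend the SAP as follows:

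- **Primary MMRM:** add the Visit 1 SANDE Global Score (SCR) as a second covariate: `model CHG = BASE SCR TRTPN AVISITN TRTPN*AVISITN`.
- **Schirmer-I ANCOVA and logistic model:** add Visit 1 Schirmer-I for the study eye. Judge any gain in the logistic analysis on the difference in proportions.
- **Staining ANCOVA:** add Visit 1 total corneal staining for the study eye.
- **Imputation:** add the corresponding Visit 1 value to the PROC MI VAR list.
- **Unchanged:** the endpoint stays change from Visit 2, with the same alpha.
- **Note to add:** for the rare patient with no Visit 2 value, BASE and SCR are the same number under SAP 4.4.1.

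The cost is one term and about one degree of freedom per model, an entry in SAP section 11 (changes in the planned analysis), and no new data. The terms must be fixed before unmasking, because covariates chosen afterwards would not be credible.

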10 STATISTICS

10.1 SAMPLE SIZE

The sample size of the study is calculated based on results from the previous study NGF0118 using the subgroup of patients with baseline SANDE Global Score > 50. Expecting a mean difference of about 11 points (with unequal standard deviations in the active and vehicle groups: observed mean changes (SD) were -28.2 (26.36) and -17.4 (20.29) for IMP and vehicle, respectively) in improvement of SANDE Global Score from baseline to Week 8 in favor of rhNGF ophthalmic (eye drop) formulation, a total sample size of 276 evaluable patients (92 per group) is needed. This will allow to achieve an overall power of 80% for demonstrating superiority of at least one concentration of rhNGF ophthalmic formulation over vehicle in the improvement of SANDE Global Score from baseline to week 8, with an overall one-sided alpha of 0.025.

The sample size calculation takes into consideration a Bonferroni correction for two comparisons (2 concentration groups versus vehicle), i.e., the alpha level has been set to 0.0125 one-sided for each comparison.

Assuming a 5% rate of patients not evaluable for primary analysis after enrollment, the total number of patients to be enrolled in the study will be about 291 (97 per group). Enrollment will be competitive.

In Dompé previous studies, a screen failure rate of about 20% has been observed (NGF0121 - PROTEGO-1). This fact implies that approximately 350 subjects will need to be screened in order to have 291 patients enrolled and at least 276 evaluable. In any case, the screen procedures should be interrupted when the expected sample size of 291 subjects has been reached.

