For patients analyzed under the hypothetical strategy (see § 3.2.1), any data collected in the week after the ICE of interest (intake of prohibited medications) will be considered as missing for the purpose of the primary analysis and will be imputed, as well as the other missing data (for example for lost to follow-up, patients who withdrew their consent), by using the multiple imputation described below with a copy-reference approach.

Missing data that may be obtained notwithstanding the intent to apply the treatment policy strategy and after having applied the hypothetical strategy when needed, will be addressed by using multiple imputation (MI) based on copy-reference approach. This approach does not assume benefits for the rhNGF in case of discontinuation and limits a post-discontinuation clinical effect to that of the vehicle. Specifically, the copy-reference approach will be implemented in this way:

- 1) Intermittent and monotone missing data for SANDE Global Score at baseline, Week 4 and Week 8 will be imputed by using the Fully Conditional Specification (FCS) method under the missing not at random (MNAR) assumption where only the subset

of observations that come from the Vehicle group are used to derive the imputation model.

- 2) For each imputed dataset, the change from baseline at Week 4 and Week 8 is derived.
- 3) The change from baseline at Week 4 and Week 8 will then be used in a MMRM as described above with change from baseline as dependent variable and baseline value, treatment arm, visit and treatment by visit interaction as independent variable. Subject will be considered as cluster variable and an unstructured covariance matrix will be set to model the within-subject correlation.
- 4) Results obtained on each imputed dataset will be combined using Rubin's rule to draw inference.

The adjusted estimated treatment difference between each concentration of the rhNGF new formulation and vehicle will be displayed together with the corresponding two-sided 95% confidence interval (CI) and one-sided p-value.

In case both concentrations of rhNGF differ from placebo, the choice between the two concentrations will be based on the size of the effect (and corresponding CI), on the results of secondary endpoints and on safety data.

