Based on this modeling, LS Mean, SE, and two-sided 95% CI at Week 4 and Week 8 will be provided for each treatment arm (rhNGF \square mcg/mL, rhNGF \square mcg/mL, and vehicle); difference in LS means, two-sided 95% CI, and corresponding one-sided p-value will be provided for each comparison at each timepoint. P-values for the comparisons at Week 8 will be used to declare the superiority of at least one of the \square over vehicle.

LS means change from baseline and corresponding 95% CI at Week 8 will be plotted in a forest plot by treatment arm for all main and sensitivity analysis.

Descriptive statistics for SANDE Global Score at each visit will be presented based on observed data and data after applying hypothetical strategy.

Primary Estimand:

Missing data that may be obtained notwithstanding the intent to apply the treatment policy strategy and after having applied the hypothetical strategy when needed (see [Section 3.3.1](#)), will be addressed by using multiple imputation (MI) based on copy-reference approach. This approach does not assume benefits for the rhNGF in case of discontinuation and limits a post-discontinuation clinical effect to that of the vehicle. Specifically, the copy-reference approach will be implemented in this way:

- Intermittent and monotone missing data for SANDE Global Score at baseline, Week 4 and Week 8 will be imputed by using the Fully Conditional Specification (FCS) method under the missing not at random (MNAR) assumption where only the subset of observations that come from the Vehicle group are used to derive the imputation model. The missing pattern is assumed to be arbitrary. The PROC MI procedure and FCS REGRESSION statement will be used with the seed of 47292748 and 50 imputed datasets. The minimum and maximum imputed values will be restrained to 0 and 100, respectively, via MIN and MAX options. In case of convergence issues, after imputation, imputed values lower than 0 or greater than 100 will be set to 0 and 100, respectively. The imputed values will be rounded to integers.
- For each imputed dataset, the change from baseline at Week 4 and Week 8 is derived.

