- The change from baseline at Week 4 and Week 8 will then be used in a MMRM as described above with change from baseline as dependent variable and baseline value, treatment arm, visit, and treatment by visit interaction as independent variable. Patient will be considered as cluster variable and an “unstructured” covariance matrix will be set to model the within-patient correlation. If convergence fails, compound symmetry matrix will be used to model the within-patient correlation.
- Results obtained on each imputed dataset will be combined using Rubin’s rule to draw inference via PROC MIANALYZE procedure. A statistical significance level of 0.0125 will be used to declare the significance of the comparisons of each treatment arm vs vehicle.

[Appendix 13.3](#) includes the SAS code for the primary analysis illustrating the key elements for the analysis.

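### The primary test is run at one-sided 0.0125 per dose, but the interval reported beside its p-value is a two-sided 95% CI, which matches a one-sided 0.025 test

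*SAP*

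**What the plan says.** **Test.** SAP section 8.1.1 sets the level for each dose: "Each comparison will be consequently tested at one-sided alpha = 0.0125, in order to preserve the overall one-sided alpha of 0.025". It repeats the level for the pooled multiple-imputation result: "A statistical significance level of 0.0125 will be used to declare the significance of the comparisons of each treatment arm vs vehicle". Protocol section 10.6.2 has the same rule.

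**Decision.** The decision rests on p-values. SAP section 8.1.1: "P-values for the comparisons at Week 8 will be used to declare the superiority of at least one of the" two concentrations over vehicle.

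**Interval.** For each dose-vehicle contrast, SAP section 8.1.1 states that "difference in LS means, two-sided 95% CI, and corresponding one-sided p-value will be provided for each comparison at each timepoint". Protocol section 10.6.2 likewise reports the adjusted difference "together with the corresponding two-sided 95% confidence interval (CI) and one-sided p-value".

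Neither document plans a 97.5% or simultaneous interval for these contrasts, and neither describes the 95% interval as unadjusted for multiplicity. The model code in SAP appendix 13.3 requests confidence limits for the differences without setting a level.

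**Other use of the interval.** If both concentrations differ from control, protocol section 10.6.2 says that "the choice between the two concentrations will be based on the size of the effect (and corresponding CI"), together with secondary endpoints and safety data.

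**The concern.** A test and the interval printed beside it should give the same answer. A two-sided 95% interval leaves 2.5% in each tail, so it lies wholly on the favourable side of zero exactly when one-sided p is below 0.025. The primary test requires p below 0.0125. Its matching interval is two-sided 97.5%.

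A dose with p between the two levels would therefore fail the primary analysis and be published with an interval that excludes zero. That invites a claim which the multiplicity plan rules out. The per-dose result has consequences: it decides which concentration goes on to Hochberg testing of the key secondary endpoints (SAP 8.2.1) and which comparison receives the conditional sensitivity analyses (SAP 8.1.2).

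The mismatch looks like a carry-over. The log of Amendment 1 in protocol section 13 shows that the per-dose level was one-sided 0.025, which a two-sided 95% CI fits exactly. The amendment halved that level and kept the 95% interval. The log only suggests the origin; the inconsistency is in the current text.

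**Working it through.** **Inputs.** Protocol 10.1: "Expecting a mean difference of about 11 points", based on "observed mean changes (SD) were -28.2 (26.36) and -17.4 (20.29) for IMP and vehicle, respectively", so the observed difference is 28.2 − 17.4 = 10.8; 92 evaluable per group; one-sided 0.0125 per comparison; 80% power; 5% not evaluable. Allocation is 1:1:1 with a shared vehicle arm. Normal approximation throughout.

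**1. Reproduce the plan's sample size.**
- Root-mean-square SD = √((26.36² + 20.29²)/2) = 23.52.
- n per group = 2 × 23.52² × (2.241 + 0.842)² / 10.8² ≈ 90.2, so 91. With a difference of 11 it is 87.
- Power at n = 92 is 80.9% for 10.8 (80.3% with the t distribution).
- 92/0.95 = 96.8, so 97 per group and 291 in total.

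The stated 92 per group and 291 are reproduced, which confirms that 0.0125 is the working level.

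**2. Where test and interval disagree.**
- SE of a difference = √((26.36² + 20.29²)/92) = 3.47.
- The 95% CI excludes zero at an observed benefit above 1.960 × 3.468 = 6.8 points.
- The primary test succeeds above 2.241 × 3.468 = 7.8 points.
- Ratio of half-widths: 2.241/1.960 = 1.14.

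**3. Chance of disagreement for one dose.** With Z ~ N(δ/SE, 1), this is Φ(2.241 − δ/SE) − Φ(1.960 − δ/SE).

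| True difference δ | δ/SE | Chance |
|---|---|---|
| 0 | 0 | 1.25% |
| 10.8 | 3.114 | 0.1914 − 0.1242 = 6.7% |
| 11 | 3.172 | 0.1761 − 0.1128 = 6.3% |

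**4. Chance that both doses fail while at least one CI excludes zero.** Assume that both doses have the same true effect. The shared vehicle arm gives a correlation between the two differences of 0.5 with equal variances, or 20.29²/(26.36² + 20.29²) = 0.37 with the planning SDs. The chance is Φ₂(2.241 − δ/SE, 2.241 − δ/SE) − Φ₂(1.960 − δ/SE, 1.960 − δ/SE), where Φ₂ is the bivariate normal distribution function.
- Correlation 0.5: 3.8% at 10.8 and 3.4% at 11.
- Correlation 0.37: 3.3% at 10.8 and 3.0% at 11.

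**5. Joint coverage of the two intervals**, P(|Z₁| < c and |Z₂| < c).

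| Correlation | Two 95% CIs (c = 1.960) | Two 97.5% CIs (c = 2.241) |
|---|---|---|
| 0 | 90.25% | 95.1% |
| 0.37 | 90.6% | 95.2% |
| 0.5 | 90.9% | 95.4% |

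A 97.5% CI lies wholly below zero exactly when one-sided p < 0.0125, so the disagreement in steps 2 to 4 disappears.

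**The case against.** The best defence is that no decision uses the interval as a test. Superiority is read from the Week 8 p-value against 0.0125, and the tipping-point analysis also uses p ≥ 0.0125. Marginal 95% intervals beside multiplicity-adjusted tests are a common convention, SAP section 4 uses 95% CIs as its general format, and neither document promises 95% joint confidence. This stands as far as error control goes. It does not remove the contradiction a reader would see in the range 6.8 to 7.8 points, because nothing tells that reader that the interval follows a different rule from the test.

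Three stronger readings are tempting, and the documents do not support them.

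- **Inflated type I error.** With no effect, the chance that at least one 95% CI favours rhNGF is 4.5% (correlation 0.5) to 4.7% (0.37), against 2.5%. That would be an error rate only if someone replaced the stated p-value rule with the interval.
- **A distorted choice of dose.** That sentence applies only if both concentrations differ from control. If this means that both passed the primary test, the 95% and 97.5% intervals all exclude zero. The choice also weighs secondary endpoints and safety. Widening both intervals by the same factor changes neither the estimates nor which interval is wider.
- **A wrong forest plot.** SAP section 8.1.1 plots LS means by treatment arm, not dose-vehicle differences, and the 0.0125 level does not apply to an arm mean.

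The reach into the sensitivity analyses is also modest: under SAP section 8.1.2 they are conditional on a significant primary comparison.

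**Conclusion.** The point holds as a mismatch between the reported interval and the decision rule. For either dose, a one-sided p-value between 0.0125 and 0.025 gives a failed test beside a CI that excludes zero. At the planning assumptions this has a 6.7% chance per dose. If both doses have the planned effect, there is a 3.4–3.8% chance at correlation 0.5 (3.0–3.3% at 0.37) that the whole trial fails while some CI excludes zero. Joint coverage of the pair is 90.6–90.9%.

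The type I error remains controlled because the p-value rule governs. The figures rest on the planning SDs, 92 evaluable per group and a normal approximation; covariate adjustment and imputation would change the SE and so the range in points. The mismatch between the two levels does not depend on those assumptions. It is worth correcting before the analysis because the correction is small, but it does not threaten the primary conclusion.

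**What to change.** In SAP section 8.1.1, report two-sided 97.5% CIs for the two Week 8 dose-vehicle differences in SANDE Global Score. Do the same in section 8.1.2 wherever a sensitivity analysis reports those differences. In SAS this is ALPHA=0.025 in LSMEANS and in PROC MIANALYZE; the MIANALYZE setting governs the pooled result. If 95% CIs are also shown, label them as unadjusted for multiplicity and state that superiority is judged by one-sided p < 0.0125. Align the sentence in protocol section 10.6.2, or record the change in SAP section 11.

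Leave the by-arm forest plot and the dose-choice text unchanged.

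The cost is a sentence or two of SAP text and one option in the code. The displayed intervals become about 14% wider. The test, sample size and data collection are unaffected.
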